5.3 Baseline Evaluation

Research and clinical laboratory tests to be performed within 4 weeks of study treatment:

5.3.1.1 Bone Marrow

1. Immunophenotyping of aberrant clonal plasma cells by multiparametric flow cytometry. Interphase fluorescence in situ hybridization (FISH)/cytogenetics.
2. Cell sorting and storage
3. Histopathological evaluation on bone marrow aspirate and biopsy
4. Immunoglobulin heavy and/or light chain rearrangement.
5. VDJ sequencing
6. Gene expression profiling
7. Whole exome sequencing
8. Immune, cellular and molecular profiling

5.3.1.2 Peripheral Blood/Urine

1. Peripheral blood and urine samples for storage.

5.4 Biospecimen collection

5.4.1 Correlative Studies

5.4.1.1 Bone Marrow

Sampling Time Points of Bone Marrow correlative studies (see Table 1)

- a) Baseline
- b) Post cycle 8
- c) Post cycle 24 (in patients receiving an additional 16 cycles of therapy only)
- d) At progression
- e) End of Study

Table 1	Baseline	Post Cycle 8 /end of study	Post Cycle 24 /end of study	Progression of Disease
Pathology/immuno- histochemistry	X	X	X	X
Multiparametric Flow Cytometry	X	X	X	X
FISH/Cytogenetics	X	X	X	X
Gene expression profiling	X			X
VDJ sequencing	X	X	X	X
Immune studies	X	X	X	X
Cytometry time of flight (CyTOF)	X	X	X	X
Whole exome sequencing	X			X
Storage	X	X	X	X

- Correlative studies associated with bone marrow specimen will be performed and related to clinical outcome if the results of the study indicate a clinical or translational rationale for analyzing the samples. Such studies may include but are not limited to the following:
 - Pathology/Immunohistochemistry: Bone marrow biopsy and aspirate will be sent to the Department of Pathology at MD Anderson Cancer Center. Immunohistochemical staining will be performed. Plasma cell burden will be assessed using immunohistochemistry markers such as CD138, light chains, CD56 etc.
 - Minimal Residual Disease:
 - Flow cytometry: Immunophenotyping of aberrant plasma cells by flow cytometry currently involves, but is not limited to, the use of the following reagents: CD138, CD19, CD45, CD38, and CD56. Characteristic changes in immunophenotypically abnormal plasma cells (CD138 positive) include but are not limited to absent CD19 and CD45, decreased CD38, and increased CD56. These studies will be performed following the Euroflow method.
 - Bone marrow, blood and urine samples, and associated clinical lab data will be sent to Adaptive Biotechnologies (Seattle, Washington) for deep sequencing of the VDJ sequence. Samples and data will be submitted to Adaptive Biotechnologies in an anonymized and de-identified manner.
 - FISH and cytogenetics: Interphase FISH/cytogenetics will be performed on patients enrolled in this protocol under the direction of the Molecular Diagnostics Core Laboratory of the Department of Pathology at MD Anderson Cancer Center

- Gene expression profiling (GEP): CD138+ plasma cells will be purified from bone marrow aspirates harvested at each indicated time point. Bone marrow samples and associated clinical lab data will be sent to Signal Genetics (Little Rock, Arkansas) for gene expression and will be analyzed to identify potential markers of early progression. Changes in selected genes may be confirmed by quantitative PCR if suggested to be related to risk of progression to MM. Samples and data will be submitted to Signal Genetics in an anonymized and de-identified manner.
- Whole exome sequencing will be performed to identify genomic alterations. Bone marrow aspirates will be done at baseline and saved at the Myeloma Tissue Bank. Peripheral blood will be collected at baseline for germ line DNA analysis.
- Characterization of T-cell and dendritic cell numbers in the bone marrow microenvironment that could contribute to immune escape and progression from SMM to symptomatic MM. These will be assessed by multiparametric flow cytometry for the following: Helper (CD4) and cytotoxic (CD8) effector T-cell differentiation subsets (naïve, effector memory, central memory, terminally differentiated, Th1, Tc1, Th2, Tc2, Th17, Tc17, Th22, Tc22), T-cell activation (CD137 (4-1BB), CD134 (OX-40), CD40L, CD69, ICOS) and inhibitory receptors (PD-1, LAG3, TIM3, CD244, CD160, BTLA, CD200R, CTLA4), T cells, NKT cells, and myeloid and plasmacytoid dendritic cells.
- Evaluation of changes in PD-L1 and PD-1 expression at baseline, end of cycle 8 and end of cycle 24 treatment and correlate with clinical response.

5.4.1.2 Research Blood/Serum and Urine

- a) At any given time, up to 50 ml of peripheral blood will be collected. The amount of blood collected will be dictated by the number of experiments to be performed, and by the patient's peripheral blood count. Typical time points include: baseline, Cycle 1, Day 2 and Day 15, then Day 1 of every cycle during cycles 2-8, end of Cycle 8, Day 1 of cycles 9-24, end of Cycle 24 and at any time point if the patient has progression of disease.
- b) At any given time, approximately 45 mL of urine will be collected into a standard urine collection cup and sent for analysis and storage at each time point. Typical time points include: baseline, Cycle 1 Day 2 and Day 15, then Day 1 of every cycle during cycles 2-8, end of Cycle 8, Day 1 of cycles 9-24, end of Cycle 24 and at any time point if the patient has progression of disease.
- c) Peripheral blood and/or urine samples from patients will be analyzed for potential serum or urine biomarkers, and correlated to clinical outcomes if the results of the study indicate a clinical or translational rationale for analyzing the samples. Such biomarkers may include but are not limited to:
 - Bone marrow, blood and urine samples, and associated clinical lab data will be sent to Adaptive Biotechnologies for deep sequencing of the VDJ sequence.

- Immune cell populations including, but not limited to T cells (CD4 and CD8), LGL, and NK cells using flow cytometry.

5.4.1.3 Procedures for genomic sequencing of samples at MD Anderson Cancer Center

- a) Sample sharing: In some cases samples may be sent to or received from outside collaborators such as Broad Institute for next-generation sequencing and/or analysis. All samples will be sent under a specific contract or Material Transfer Agreement (MTA). We will protect participant's privacy by coding samples and keeping the master list of identifiers accessible to only key project staff. Data will be kept on secure computers and samples will be kept in freezers in locked laboratories and buildings. Additionally in some other cases, samples may be provided from outside collaborators or institutions for discovery and research purposes. In such cases, the samples should be obtained under IRB-approved protocols at these outside collaborators and institutions to allow them for participation in this protocol and under a specific grant/ contract or Material Transfer Agreement (MTA) with MD Anderson Cancer Center.
- b) Internal/External Sequencing may be done here at MD Anderson, in one of the Core labs such as Cancer Genomics Lab, but in some cases samples may be sent to outside collaborators for sequencing and/or analysis such as Broad Institute. Sequencing performed by Broad or any other external collaborator will be conducted under specific contract or Material Transfer Agreement (MTA).
- c) Data Sharing/Deposition: Researchers can do more powerful studies when they share with each other the information they get from studying human samples. Next generation sequencing data may be placed in a local M.D. Anderson Institutional Data Repository (IDR), such as the access controlled BigData; where both deposition of and access to data require governance and approval. In some cases, grant requirements may require deposition of large-scale data into the public Genotypes and Phenotypes database (dbGaP) an access controlled database overseen by the National Center for Biotechnology Information (NCBI). In other cases peer reviewed Journals may require data to be shared through a resource such as dbGaP. Data submitted to those repositories will only be shared in a de-identified fashion and without associated clinical data or identifiers. This data will be used only for research purposes, and the data elements collected and analyzed will only be those that are necessary to conduct this research.
- d) Database access additional protections: The precedent to publically broadcast sequence data has been set by large consortial projects, such as The Cancer Genome Atlas (TCGA) and the Encyclopedia of DNA Elements (ENCODE), in order to maximize data utility. However, we know there is the potential for privacy risks associated with the release of sequence data to databases and while the risk may be small it could grow in the future as technology advances. To minimize this potential, we will implement good faith efforts to ensure patient confidentiality and reduce patient exposure. The database of Genotypes and Phenotypes and others like it are extremely access restricted. Only authorized researchers may deposit or access the data and either or both efforts require MD Anderson institutional approval. Sequence data will only be broadcast through secure transmission processes. All samples will be de-identified with access to the linking table available

only to the MD Anderson PI and his/her designees. Only non-identifiable data will be deposited to dbGaP i.e., no linking table or access to a linking table will be available. Research records will be kept separate from medical records and patients will not have access to any of the research data.

- e) Protected health information (PHI) may be collected from medical records that are related to health and/or disease history including test results, medical procedures, and images (such as X-rays) in addition demographic and environmental factors may be requested. Researchers will use this information to better understand how genes affect health and response to treatment. All samples will be de-identified with access to the linking table available only to the MD Anderson PI and his/her designees.

5.5 Registration Procedures

The Investigator must obtain documented consent from each potential subject prior to participating in a clinical trial.

5.6 Monitoring

5.6.1 Study Monitoring

The University of Texas MD Anderson Cancer Center IND Office will monitor the study investigators to assure satisfactory enrollment rate, data recording, and protocol adherence. The site principal investigator and staff are expected to cooperate and provide all relevant study documentation in detail at each site visit on request for review. MD Anderson Cancer Center will monitor and/or audit the other participating sites to assure satisfactory protocol adherence and enrollment.

5.6.1.1 Patients will be observed in the infusion center after administration of cycle 1 Day 1 of therapy at least for 2 hours after receiving the infusion.

5.6.1.2 Routine labs (CBC with differential, chemistry panel and mineral panel, LDH, magnesium, uric acid, phosphate) will be performed on Day 1 of each cycle. Myeloma tests include serum protein electrophoresis, serum immunofixation, 24 hour urine protein electrophoresis and immunofixation, serum free light chains, quantitative immunoglobulins and beta-2 microglobulin will be performed at baseline and Day 1 of each cycle.

5.6.1.3 Patients will have clinic visits with H&P or standard progress notes assessing for toxicity/side effects on Day 1 of cycle 1 and Day 1 of each cycle thereafter.

5.6.1.4 Additional laboratory studies and clinic visits will be performed if clinically indicated.

5.7 Trial Treatments

The treatment to be used in this trial is outlined below in Table 2

Table 2 Trial Treatment

Drug	Dose/Potency	Dose Frequency	Route of Administration	Regimen/Treatment Period	Use
Pembrolizumab	200 mg	Q3W	IV infusion	Day 1 every 21 days	Experimental

5.7.1 Dose Selection/Modification

5.7.1.1 Dose Selection

Dose selection is based on the current FDA approved dose of pembrolizumab¹⁰.

5.7.1.2 Dose Modification

Adverse events (both non-serious and serious) associated with pembrolizumab exposure may represent an immunologic etiology. These adverse events may occur shortly after the first dose or several months after the last dose of treatment.

Pembrolizumab must be withheld for drug-related serious adverse events grade 4 or higher or intolerable side effects.

Additionally, pembrolizumab must be withheld for drug-related toxicities and severe or life-threatening AEs as per Table 3 below. See Section 5.9 and Events of Clinical Interest Guidance Document for supportive care guidelines, including use of corticosteroids.

Table 3

Dose Modification Guidelines for Drug-Related Adverse Events

Toxicity	Hold Treatment For Grade	Timing for Restarting Treatment	Discontinue Subject
Diarrhea/Colitis	2-3	Toxicity resolves to Grade 0-1.	Toxicity does not resolve within 12 weeks of last dose or inability to reduce corticosteroid to 10 mg or less of prednisone or equivalent per day within 12 weeks.
	4	Permanently discontinue	Permanently discontinue
AST, ALT, or Increased Bilirubin	2	Toxicity resolves to Grade 0-1	Toxicity does not resolve within 12 weeks of last dose.
	3-4	Permanently discontinue (see exception below) ¹	Permanently discontinue
Type 1 diabetes mellitus (if new onset) or Hyperglycemia	T1DM or 3-4	Hold pembrolizumab for new onset Type 1 diabetes mellitus or Grade 3-4 hyperglycemia associated with evidence of beta cell failure.	Resume pembrolizumab when patients are clinically and metabolically stable.
Hypophysitis	2-3	Toxicity resolves to Grade 0-1	Toxicity does not resolve within 12 weeks of last dose or inability to reduce corticosteroid to 10 mg or less of prednisone or equivalent

Toxicity	Hold Treatment For Grade	Timing for Restarting Treatment	Discontinue Subject
			per day within 12 weeks.
	4	Permanently discontinue	Permanently discontinue
Hyperthyroidism	3	Toxicity resolves to Grade 0-1	Toxicity does not resolve within 12 weeks of last dose or inability to reduce corticosteroid to 10 mg or less of prednisone or equivalent per day within 12 weeks.
	4	Permanently discontinue	Permanently discontinue
Hypothyroidism	2-4	Therapy with pembrolizumab can be continued while treatment for the thyroid disorder is instituted	Therapy with pembrolizumab can be continued while treatment for the thyroid disorder is instituted.
Infusion Reaction	3-4	Permanently discontinue	Permanently discontinue
Pneumonitis	2	Toxicity resolves to Grade 0-1	Toxicity does not resolve within 12 weeks of last dose or inability to reduce corticosteroid to 10 mg or less of prednisone or equivalent per day within 12 weeks.
	3-4	Permanently discontinue	Permanently discontinue
Renal Failure or Nephritis	2	Toxicity resolves to Grade 0-1	Toxicity does not resolve within 12 weeks of last dose or inability to reduce corticosteroid to 10 mg or less of prednisone or equivalent per day within 12 weeks.
	3-4	Permanently discontinue	Permanently discontinue
All Other Drug-Related Toxicity ²	3 or Severe	Toxicity resolves to Grade 0-1	Toxicity does not resolve within 12 weeks of last dose or inability to reduce corticosteroid to 10 mg or less of prednisone or equivalent per day within 12 weeks.
	4	Permanently discontinue	Permanently discontinue
Note: Permanently discontinue for any severe or Grade 3 drug-related AE that recurs or any life-threatening event.			
¹ For patients with liver metastasis who begin treatment with Grade 2 AST or ALT, if AST or ALT increases by greater than or equal to 50% relative to baseline and lasts for at least 1 week then patients should be discontinued.			
² Patients with intolerable or persistent Grade 2 drug-related AE may hold study medication at physician discretion. Permanently discontinue study drug for persistent Grade 2 adverse reactions for which treatment with study drug has been held, that do not recover to Grade 0-1 within 12 weeks of the last dose.			

Dosing interruptions are permitted in the case of medical / surgical events or logistical reasons not related to study therapy (e.g., elective surgery, unrelated medical events, patient vacation, and/or holidays). Subjects should be placed back on study therapy within 3 weeks of the scheduled interruption, unless otherwise discussed with the Sponsor. The reason for interruption should be documented in the patient's study record.

5.7.2 Timing of Dose Administration

Trial treatment should be administered on Day 1 of each cycle after all procedures/assessments have been completed as detailed on the Study Calendar (Section 7.0). Trial treatment may be administered up to 3 days before or after the scheduled Day 1 of each cycle due to administrative reasons.

All trial treatments will be administered on an outpatient basis.

Pembrolizumab 200 mg will be administered as a 30 minute IV infusion every 3 weeks. Every effort should be made to target infusion timing to be as close to 30 minutes as possible. However, given the variability of infusion pumps, a window of -5 minutes and +10 minutes is permitted (i.e., infusion time is 30 minutes: -5 min/+10 min).

The Pharmacy Manual contains specific instructions for the preparation of the pembrolizumab infusion fluid and administration of infusion solution.

5.8 Concomitant Medications/Vaccinations (allowed & prohibited)

Medications or vaccinations specifically prohibited in the exclusion criteria are not allowed during the ongoing trial. If there is a clinical indication for one of these or other medications or vaccinations specifically prohibited during the trial, discontinuation from trial therapy or vaccination may be required. The investigator should discuss any questions regarding this with the Merck Clinical team. The final decision on any supportive therapy or vaccination rests with the investigator and/or the subject's primary physician.

5.8.1 Acceptable Concomitant Medications

All treatments that the investigator considers necessary for a subject's welfare may be administered at the discretion of the investigator in keeping with the community standards of medical care. All concomitant medication will be recorded in the medical record including all prescription, over-the-counter (OTC), herbal supplements, and IV medications and fluids. If changes occur during the trial period, documentation of drug dosage, frequency, route, and date may also be included in the medical record.

All concomitant medications received within 28 days before the first dose of trial treatment and 30 days after the last dose of trial treatment should be recorded. Concomitant medications administered after 30 days after the last dose of trial treatment should be recorded for SAEs and ECIs as defined in Section 8.2.

5.8.2 Prohibited Concomitant Medications

Subjects are prohibited from receiving the following therapies during the Screening and Treatment Phase (including retreatment for post-complete response relapse) of this trial:

- Antineoplastic systemic chemotherapy or biological therapy
- Immunotherapy not specified in this protocol
- Chemotherapy not specified in this protocol
- Investigational agents other than pembrolizumab
- Radiation therapy
- Live vaccines within 30 days prior to the first dose of trial treatment and while participating in the trial. Examples of live vaccines include, but are not limited to, the following: measles, mumps, rubella, varicella/zoster, yellow fever, rabies, BCG, and typhoid vaccine.
- Systemic glucocorticoids for any purpose other than to modulate symptoms from an event of clinical interest of suspected immunologic etiology. The use of physiologic doses of corticosteroids may be approved after consultation with the Sponsor.

Subjects who, in the assessment by the investigator, require the use of any of the aforementioned treatments for clinical management should be removed from the trial. Subjects may receive other medications that the investigator deems to be medically necessary.

The Exclusion Criteria describes other medications which are prohibited in this trial.

There are no prohibited therapies during the Post-Treatment Follow-up Phase.

5.9 Rescue Medications & Supportive Care

5.9.1 Supportive Care Guidelines

Subjects should receive appropriate supportive care measures as deemed necessary by the treating investigator. Suggested supportive care measures for the management of adverse events with potential immunologic etiology are outlined below and in greater detail in the ECI guidance document. Where appropriate, these guidelines include the use of oral or intravenous treatment with corticosteroids as well as additional anti-inflammatory agents if symptoms do not improve with administration of corticosteroids. Note that several courses of steroid tapering may be necessary as symptoms may worsen when the steroid dose is decreased. For each disorder, attempts should be made to rule out other causes such as metastatic disease or bacterial or viral infection, which might require additional supportive care. The treatment guidelines are intended to be applied when the investigator determines the events to be related to pembrolizumab.

Note: if after the evaluation the event is determined not to be related, the investigator is instructed to follow the ECI reporting guidance but does not need to follow the treatment guidance (as outlined in the ECI guidance document). Refer to Section 5.7.1.2 for dose modification.

It may be necessary to perform conditional procedures such as bronchoscopy, endoscopy, or skin photography as part of evaluation of the event. Suggested conditional procedures, as appropriate, can be found in the ECI guidance document.

- **Pneumonitis:**

- For **Grade 2 events**, treat with systemic corticosteroids. When symptoms improve to Grade 1 or less, steroid taper should be started and continued over no less than 4 weeks.
- For **Grade 3-4 events**, immediately treat with intravenous steroids. Administer additional anti-inflammatory measures, as needed.
- Add prophylactic antibiotics for opportunistic infections in the case of prolonged steroid administration.

- **Diarrhea/Colitis:**

Subjects should be carefully monitored for signs and symptoms of enterocolitis (such as diarrhea, abdominal pain, blood or mucus in stool, with or without fever) and of bowel perforation (such as peritoneal signs and ileus).

- All subjects who experience diarrhea/colitis should be advised to drink liberal quantities of clear fluids. If sufficient oral fluid intake is not feasible, fluid and electrolytes should be substituted via IV infusion. For Grade 2 or higher diarrhea, consider GI consultation and endoscopy to confirm or rule out colitis.
- For **Grade 2 diarrhea/colitis** that persists greater than 3 days, administer oral corticosteroids.

- For **Grade 3 or 4 diarrhea/colitis** that persists > 1 week, treat with intravenous steroids followed by high dose oral steroids.
- When symptoms improve to Grade 1 or less, steroid taper should be started and continued over no less than 4 weeks.

- **Type 1 diabetes mellitus (if new onset, including diabetic ketoacidosis [DKA]) or ≥ Grade 3 Hyperglycemia, if associated with ketosis (ketonuria) or metabolic acidosis (DKA)**
 - For **T1DM** or **Grade 3-4 Hyperglycemia**
 - Insulin replacement therapy is recommended for Type I diabetes mellitus and for Grade 3-4 hyperglycemia associated with metabolic acidosis or ketonuria.
 - Evaluate patients with serum glucose and a metabolic panel, urine ketones, glycosylated hemoglobin, and C-peptide.

- **Hypophysitis:**
 - For **Grade 2** events, treat with corticosteroids. When symptoms improve to Grade 1 or less, steroid taper should be started and continued over no less than 4 weeks. Replacement of appropriate hormones may be required as the steroid dose is tapered.
 - For **Grade 3-4** events, treat with an initial dose of IV corticosteroids followed by oral corticosteroids. When symptoms improve to Grade 1 or less, steroid taper should be started and continued over no less than 4 weeks. Replacement of appropriate hormones may be required as the steroid dose is tapered.

- **Hyperthyroidism or Hypothyroidism:**

Thyroid disorders can occur at any time during treatment. Monitor patients for changes in thyroid function (at the start of treatment, periodically during treatment, and as indicated based on clinical evaluation) and for clinical signs and symptoms of thyroid disorders.

 - **Grade 2** hyperthyroidism events (and **Grade 2-4** hypothyroidism):
 - In hyperthyroidism, non-selective beta-blockers (e.g. propranolol) are suggested as initial therapy.
 - In hypothyroidism, thyroid hormone replacement therapy, with levothyroxine or liothyronine, is indicated per standard of care.
 - **Grade 3-4** hyperthyroidism
 - Treat with an initial dose of IV corticosteroid followed by oral corticosteroids. When symptoms improve to Grade 1 or less, steroid taper should be started and continued over no less than 4 weeks. Replacement of appropriate hormones may be required as the steroid dose is tapered.

- **Hepatic:**

- For **Grade 2** events, monitor liver function tests more frequently until returned to baseline values (consider weekly).
 - Treat with IV or oral corticosteroids
 - For **Grade 3-4** events, treat with intravenous corticosteroids for 24 to 48 hours.
 - When symptoms improve to Grade 1 or less, a steroid taper should be started and continued over no less than 4 weeks.
- **Renal Failure or Nephritis:**
 - For **Grade 2** events, treat with corticosteroids.
 - For **Grade 3-4** events, treat with systemic corticosteroids.
 - When symptoms improve to Grade 1 or less, steroid taper should be started and continued over no less than 4 weeks.

Management of Infusion Reactions: Signs and symptoms usually develop during or shortly after drug infusion and generally resolve completely within 24 hours of completion of infusion.

Table 4 below shows treatment guidelines for subjects who experience an infusion reaction associated with administration of pembrolizumab.

Table 4 Infusion Reaction Treatment Guidelines

NCI CTCAE Grade	Treatment	Premedication at subsequent dosing
Grade 1 Mild reaction; infusion interruption not indicated; intervention not indicated	Increase monitoring of vital signs as medically indicated until the subject is deemed medically stable in the opinion of the investigator.	None
Grade 2 Requires infusion interruption but responds promptly to symptomatic treatment (e.g., antihistamines, NSAIDS, narcotics, IV fluids); prophylactic medications indicated for <=24 hrs	Stop Infusion and monitor symptoms. Additional appropriate medical therapy may include but is not limited to: IV fluids Antihistamines NSAIDS Acetaminophen Narcotics Increase monitoring of vital signs as medically indicated until the subject is deemed medically stable in the opinion of the investigator. If symptoms resolve within one hour of stopping drug infusion, the infusion may be restarted at 50% of the original infusion rate (e.g., from 100 mL/hr to 50 mL/hr). Otherwise dosing will be held until symptoms resolve and the subject should be premedicated for the next scheduled dose. Subjects who develop Grade 2 toxicity despite adequate premedication should be permanently discontinued from further trial treatment administration.	Subject may be premedicated 1.5h (± 30 minutes) prior to infusion of pembrolizumab (MK-3475) with: Diphenhydramine 50 mg po (or equivalent dose of antihistamine). Acetaminophen 500-1000 mg po (or equivalent dose of antipyretic).
Grades 3 or 4 Grade 3: Prolonged (i.e., not rapidly responsive to symptomatic medication and/or brief interruption of infusion); recurrence of symptoms following	Stop Infusion. Additional appropriate medical therapy may include but is not limited to: IV fluids Antihistamines NSAIDS Acetaminophen	No subsequent dosing

NCI CTCAE Grade	Treatment	Premedication at subsequent dosing
initial improvement; hospitalization indicated for other clinical sequelae (e.g., renal impairment, pulmonary infiltrates) Grade 4: Life-threatening; pressor or ventilatory support indicated	Narcotics Oxygen Pressors Corticosteroids Epinephrine Increase monitoring of vital signs as medically indicated until the subject is deemed medically stable in the opinion of the investigator. Hospitalization may be indicated. Subject is permanently discontinued from further trial treatment administration.	
Appropriate resuscitation equipment should be available in the room and a physician readily available during the period of drug administration.		

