multicenter, open-label, randomized (1:1) early phase clinical trial of 173 patients with unresectable or metastatic melanoma¹¹. Patients were treated in two cohorts of pembrolizumab 2 mg/kg (n=8) and 10 mg/kg (n=84) intravenously every 3 weeks until disease progression or unacceptable toxicity. Efficacy endpoints were overall response rate (ORR) assessed by Response Evaluation Criteria in Solid Tumors (RECIST v1.1) by independent central review. The ORR was 26% in both cohorts (p=0.96). Median duration of response was not reached in either dose group at time of study publication (range >6 weeks to >37 weeks). The safety profiles were similar between the two dosing cohorts. Drug-related adverse events (AE) occurred in 82% of patients in either dose group. However, drug-related grade 3 or 4 AE occurred in only 12% of patients. The only drug-related grade 3 to 4 AE that occurred in more than one patient was fatigue (3%). The most common drug-related AE of all grades were fatigue, pruritus and rash. Grade 3 or 4 immune-mediated AE occurred in 1.7% of patients: autoimmune hepatitis, maculopapular rash and pancreatitis. Other special interest grade 3 or 4 drug-related AEs occurred in 6% of patients: autoimmune hepatitis, diarrhea, hypophysitis, maculopapular rash, pancreatitis, rash and pneumonitis. These were generally manageable with treatment interruption and corticosteroid treatment. Only 2.3% of patients discontinued treatment because of AE that were immune related or of special interest.

Most MM cells express PD-L1 which might represent a mechanism of tumor immune evasion¹². By blocking the interactions between PD-L1/PD-L2 and PD-1, pembrolizumab may be able to reactivate immune surveillance leading to improved anti-tumor activity. Several clinical trials (NCT01953692, NCT02036502, NCT02289222 and NCT02331368) (www.clinicaltrials.gov) are currently ongoing either in the post-transplant or relapsed/refractory setting, with pembrolizumab single agent or in combination with lenalidomide and pomalidomide.

Refer to the Investigator's Brochure (IB)/approved labeling for detailed background information on MK-3475.

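### The diarrhea/colitis guidance in 5.9.1 starts corticosteroids later for grade 3-4 events (after more than 1 week) than for grade 2 events (after more than 3 days)

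*Combined protocol and SAP*

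**What the plan says.** Section 5.9.1 (Supportive Care Guidelines) lists suggested management by organ system. Two neighbouring bullets under diarrhea/colitis set the steroid triggers:

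- Grade 2: "that persists greater than 3 days, administer oral corticosteroids".
- Grade 3 or 4: "that persists > 1 week, treat with intravenous steroids followed by high dose oral steroids".

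The rest of the diarrhea/colitis text covers monitoring for enterocolitis and bowel perforation, oral or intravenous fluids, considering a GI consultation and endoscopy from grade 2 upward, and the steroid taper. None of it starts steroids earlier at grade 3-4.

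Elsewhere in 5.9.1, the grade 3-4 pneumonitis rule is "immediately treat with intravenous steroids" and the grade 3-4 hepatic rule is "treat with intravenous corticosteroids for 24 to 48 hours". Section 5.7.1.2, Table 3 ("Dose Modification Guidelines for Drug-Related Adverse Events") holds pembrolizumab for grade 2-3 diarrhea/colitis and stops it permanently at grade 4. For steroid use, 5.7.1.2 refers back to Section 5.9 and to the ECI guidance document.

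**The concern.** Guidance on immune-related toxicity normally becomes more urgent as the grade rises. Table 3 follows that pattern for dosing, but the steroid timing in the diarrhea/colitis bullets runs the other way.

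Section 5.9.1 is the steroid guidance in the body of the protocol, and it is where a site will look when an event occurs. An investigator who follows it literally would treat a grade 2 case on day 4 and leave a grade 3 or 4 case without steroids until day 8. The same section asks sites to watch for bowel perforation, and Table 5 (Section 8.2.4) describes grade 4 as needing urgent intervention. The trial enrols asymptomatic patients, for whom avoidable harm from treatment is hard to justify.

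What is at stake is patient safety in a rare event. The sample size, the stopping rule, the primary endpoint and the way toxicity is counted are not affected.

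**Working it through.** The plan gives no figure to reproduce. The check sets the written triggers side by side, converts them to days, and then asks how often the event might arise.

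**1. Trigger dates (5.9.1), with onset as day 1 and the grade constant from onset**

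| Grade | Written condition | First day met | Treatment |
|---|---|---|---|
| 2 | more than 3 days | day 4 | oral corticosteroids |
| 3-4 | more than 1 week (7 days) | day 8 | IV steroids, then high-dose oral |

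Gap: 8 − 4 = 4 days (days 4, 5, 6 and 7). Counting elapsed days gives the same difference: 7 − 3 = 4.

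**2. Other grade 3-4 steroid rules in 5.9.1**

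| Event | Waiting period before steroids at grade 3-4 |
|---|---|
| Pneumonitis | none; immediate |
| Hypophysitis | none stated |
| Hyperthyroidism | none stated |
| Hepatic | none stated |
| Renal failure or nephritis | none stated |
| Diarrhea/colitis | more than 1 week |

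**3. Search for an earlier grade 3-4 trigger.** Table 3 governs holding and stopping the drug, not starting steroids. Section 5.8.1 allows any treatment the investigator considers necessary. Section 5.8.2 exempts steroids for suspected immune-related events from the prohibited list. These sections permit earlier steroids, but none of them sets a time to start.

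**4. Expected frequency.** The only rate information is the melanoma trial summarized in Section 4.1 (173 patients). Applying it to smoldering myeloma is an assumption.

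- Section 4.1 says fatigue was the only drug-related grade 3-4 event seen in more than one patient. Grade 3-4 diarrhea therefore occurred in at most 1 of 173: p = 1/173 = 0.0058.
- Expected among 16 patients: 16 × 0.0058 = 0.09.
- Chance of at least one case: 1 − (172/173)^16 = 0.089, about 9%.
- Section 4.1 also gives 6% for grade 3-4 special-interest events, pooled over seven types of which diarrhea is one. That gives 16 × 0.06 = 0.96 expected events of all seven types together. It is a ceiling, not a rate for diarrhea.
- The two statements do not fully agree: one patient for each of seven types would be 7/173 = 4.0%, not 6%. On either statement, fewer than one grade 3-4 diarrhea case is expected among 16 patients.

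These figures count any grade 3-4 diarrhea. The documents do not allow an estimate of how many cases would last into days 4-7 with steroids withheld because of this bullet.

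**The case against.** **The measures are discretionary.** Section 5.9.1 opens with "Subjects should receive appropriate supportive care measures as deemed necessary by the treating investigator", and 5.8.1 says treatments "may be administered at the discretion of the investigator in keeping with the community standards of medical care". Nothing obliges anyone to wait. A hospitalized case would also be a serious adverse event, reportable to the sponsor within 24 hours under 8.2.3.1. All of this is true, and it limits the harm. It does not make the suggested order right.

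**The ECI guidance document may already set an earlier trigger.** Section 5.9.1 cites it for more detail, and Section 12.2 identifies version 5.0 as appendix 1. It was not available for this review, so this possibility stands. If it does set an earlier trigger, the protocol body disagrees with its own appendix and still needs correcting. If it does not, the inversion is in both.

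**The one-week line may be an escalation step, and its clock is undefined.** The two bullets name different treatments, and the text does not say whether the week runs from the onset of diarrhea or from reaching grade 3. The escalation reading fails because no earlier grade 3-4 steroid step is written for it to follow. The point about the clock is fair. A patient with more than 3 days at grade 2 before worsening has already met the oral trigger, so the 4-day figure belongs to events that are grade 3-4 from onset. The ambiguity also cuts the other way: a patient who reaches grade 3 on day 3 would, on a clock that starts at grade 3, wait until day 3 + 7 = day 10.

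**Some delay may be deliberate in this organ system.** The grade 2 bullet also has a wait, unlike the grade 2 steroid rules for pneumonitis, hypophysitis, hepatic and renal events, and 5.9.1 asks that infection be ruled out. That could justify a short wait at grade 3-4. It cannot justify a longer one than at grade 2.

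**Conclusion.** The concern holds. As written, the diarrhea/colitis bullets give the more severe event a steroid trigger 4 days later than the milder one, and nothing else in the available text repairs this. The 4 days assume an event at grade 3-4 from onset and a literal reading of both bullets.

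Only the steroid trigger is affected. Fluids, consideration of GI work-up, and the dose holds and discontinuations in Table 3 still apply. The event is likely to be rare, with about a 9% chance of any case among 16 patients if the melanoma count carries over; that count rests on at most one patient and is imprecise.

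This is a wording defect in safety guidance that should be corrected, and it does not threaten the trial's validity. The main uncertainty is what the ECI guidance document says.

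**What to change.** Reword the grade 3-4 diarrhea/colitis bullet in 5.9.1 so that its steroid trigger is never later than the grade 2 trigger. There are two ways to do this:

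1. Delete the one-week condition, which brings the bullet into line with the other grade 3-4 steroid rules in the section.
2. If a short interval is wanted to exclude infection, replace it with a limit set by the medical monitor that is no longer than the grade 2 limit of 3 days, and state that it runs from the onset of diarrhea.

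In either case, check the new wording against ECI guidance document version 5.0 and make the two agree.

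The cost is a one-line change by amendment or clarification letter, plus that check. No patients, visits or procedures are added, and the statistical section is unchanged.
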